10.2 Sample Size Considerations

The study team plans for a 20% participant dropout or incompletion rate. For this reason, they will enroll 25 study participants when in actuality they need 20 study participants to complete the study. If 20 study participants complete the study and there are still 5 active participants, the active participants will still complete the study.

This is **not** a clinical trial to investigate the efficacy of the therapy for the treatment of IBS-C. Instead, this is a pilot study to determine which method of TEA (4 different modalities and 1 placebo) is more effective in treating abdominal pain in patients with IBS-C by studying patients' sensation to rectal distention with different methods of treatment. The findings of this pilot study will be used to determine which treatment to use in a future clinical trial. No preliminary data are available for the calculation of the sample size. The sample size stated in this study was based the PI's experience in other neuromodulation studies involving methodological optimization.

10.2.1 Safety Review

Study enrollment and/or study visits will halt to at if the study team feels the study is unsafe. This would include if study participants are experiencing serious adverse events. The DSMB will meet every 3 months during the study enrollment/study visit period. If needed, the DSMB will meet more frequently to monitor the study.

This is an acute study involving 5 sessions on separate days. No treatment or intervention will be given in between sessions.

The risks involved in the study include rectal distention (a clinically approval procedure) and delivery of weak electrical current via skin surface electrodes. Any acute study session will be terminated if the patient is not tolerable to the procedure or decides to withdraw. If the safety is a concern, the remaining

study sessions will be cancelled for that particular subject. The study enrollment will be halted if serious adverse events are reported.

Safety outcome measures will include 1) pain/discomfort level during rectal distention, 2) any signs or symptoms of possible perforation or rupturing of the rectum during insertion of the rectal catheter and during rectal balloon distention, 3) any side effects due to weak electrical stimulation, such as rash or discomfort in the area of stimulation.

10.2.2 Efficacy Review

This pilot study does not assess efficacy of the proposed TEA treatment.

The study outcomes include rectal sensation and pain during rectal distention, autonomic functions noninvasively assessed from the ECG.

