3.1 Study Objectives

The objectives of this study are as follows:

- To understand the impact of TEA on study participants with IBS-C (reduction of pain related to IBS-C)
- Assess the safety of TEA in study participants with IBS-C
- Refine which (if any) TEA stimulation and location combination delivers the greatest reduction in pain associated with IBS-C

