3.2.2 Secondary Outcome Measures

A secondary outcome of the study will be reviewing the volume and pressure measurements from the barostat device. The surveys will also be reviewed to see if the study participants have a change in their symptoms.

4 Study Design

This is a placebo-controlled trial. The placebo is the sham-TEA visit. The study will recruit 25 study participants with IBS-C. These study participants will be recruited from the UM Health Research Recruiting Registry (UM HealthResearch.org), Michigan Bowel Control Program (MBCP), Functional Bowel Disease (FBD), and the study team will screen the gastroenterology clinic schedules via MiChart.

This is a phase 1 trial. This study will only occur at the University of Michigan. There is only one group/arm of study participants. The study team plans to complete enrollment within 12 months of beginning to the study. Study participant participation will be at a minimum 5 weeks (1 week between

visits) and at a maximum 15 weeks (3 weeks between each visit). The test agent is the novel TEA device.

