9.4 Safety Oversight

Data and Safety Monitoring Board (DSMB)

The first DSMB meeting will occur one month after recruitment begins. In addition to reviewing Serious Adverse Events (SAEs), the first DSMB meeting will focus on over all safety of the trial and study agent and will make a determination as to whether or not the study should proceed. The DSMB will then meet once every 6 months throughout the remainder of the study and at any time during the study in which an unexpected and possibly related SAE occurs.

The DSMB will be composed of the following members:

[name]: a Gastroenterologist and Professor of Medicine from the Division of Gastroenterology, Texas Tech University Health Science Center. [name] is an established clinical investigator in the field of functional gastrointestinal diseases. She will serve as the Chair of the committee.

[name]: a Gastroenterologist and [name]., Chair in Gastroenterology Gastrointestinal Motility Clinic from the Division of Gastroenterology at the University of Louisville. [name] is an expert in functional gastrointestinal diseases and has extensive experience in clinical trials and clinical research. He will serve as a member of the committee.

[name], PhD: an Assistant Professor of Medicine and Director of Gastrointestinal Motility, Division of Gastroenterology and Hepatology MetroHealth Medical Center, Case Western Reserve University, Cleveland, Ohio. He will serve as a member of the committee

[name]: a lead statistician from University of Michigan, Michigan Institute for Clinical & Health Research. He has over 15 years of experience on translational and health research projects across various disease area. He will serve as a member of the committee.

10 Statistical Considerations

Analysis of variance (ANOVA) will be performed to investigate the difference in each of the outcomes among 4 different sessions. Tukey's test will be used for study the differences in each of the measurements between two stimulation points (same stimulation parameters) and between two stimulation parameter sets (same stimulation points). The Pearson correlation analysis will also be performed to investigate the correlation between each of HRV parameters and the pain score or sensation threshold

. 10.1 Study Hypotheses

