TEA at acupoints ST36 (a point below the knee cap) or PC6 (a point in the wrist) will be effective in reducing abdominal pain induced by rectal distention in patients with IBS-C. This hypothesis is based on published literature and our [name] experience with EA and TEA at the Johns Hopkins. [name] previous experience with EA and TEA includes: animal studies in which electrical acupuncture at ST36/PC was shown to reduce abdominal pain in a rodent model of IBS and functional dyspepsia and preliminary clinical study in patients with IBS-C showing the reduction of overall symptoms of IBS, including abdominal pain.

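### The analysis names no comparison of the TEA modalities with sham, so the plan prespecifies no route to concluding that none of them beats sham

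*Combined protocol and SAP*

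**What the plan says.** Four places in the protocol point to a comparison with sham:

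- Section 3.1 lists as an objective: "Refine which (if any) TEA stimulation and location combination delivers the greatest reduction in pain associated with IBS-C". The parenthesis makes none an admissible answer.
- Section 4 states: "This is a placebo-controlled trial. The placebo is the sham-TEA visit". Every participant has a sham visit (5.4.1).
- Section 10.1 hypothesises that TEA at ST36 or PC6 "will be effective in reducing abdominal pain induced by rectal distention in patients with IBS-C".
- Section 10.2 gives the aim as "to determine which method of TEA (4 different modalities and 1 placebo) is more effective in treating abdominal pain in patients with IBS-C", which counts the placebo among the methods. It adds: "The findings of this pilot study will be used to determine which treatment to use in a future clinical trial".

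The analysis text does not follow through. The opening of section 10 uses ANOVA to "investigate the difference in each of the outcomes among 4 different sessions". Section 10.3 repeats the sentence without a number of sessions. In both, Tukey's test is assigned to two kinds of pair: the two points at the same parameters, and the two parameter sets at the same point. Neither kind involves sham.

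On efficacy, 10.2 says that the study is not "a clinical trial to investigate the efficacy of the therapy for the treatment of IBS-C". Section 10.2.2 drops that limit: "This pilot study does not assess efficacy of the proposed TEA treatment". Its next sentence lists rectal sensation and distension pain among the outcomes, and pain is what 10.1 is about.

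**The concern.** A ranking of four modalities always has a top entry, whether or not any of them does more than sham. If the named contrasts only set active modalities against each other, the result says which is ahead but not whether the leader does anything. That is the question in 10.1 and in the parenthesis of 3.1, and it matters because 10.2 makes choosing the next trial's treatment the purpose of the pilot.

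Section 3.2.1 does not fill the gap. It judges success by the rise in maximum tolerance from before to after TEA within a visit, without reference to the same change at the sham visit.

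The unqualified sentence in 10.2.2 adds doubt. A reader cannot tell whether the acute effect on distension pain is to be assessed or is disclaimed along with clinical efficacy.

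**Working it through.** **The plan's own figure.** Section 10.2 needs 20 completers and allows 20% dropout: 20 / (1 − 0.20) = 25, the stated enrolment. It reproduces. The 20 has no alpha, power, effect size or SD behind it (10.2 says no preliminary data exist), so there is no power figure to check.

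**Where sham enters the plan.**

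| Place | Role of sham |
|---|---|
| 3.1, 4, 10.1, 10.2 | Stated or implied comparator |
| Section 10, ANOVA | Four sessions; five are run, and which four is not said |
| Section 10.3, ANOVA | Number of sessions not given; can include sham |
| Sections 10 and 10.3, Tukey | No sham pair named |
| 10.2, choice of treatment | No criterion that refers to sham |

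**Assumptions for the figures below.** 20 completers; independent normal session errors; no period or carryover effects; effects in units of the within-participant residual SD. The documents give no SD, so the effect sizes are assumed and shown as a range.

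**Four-session ANOVA.** Suppose the four sessions are the active ones. If all four modalities beat sham by the same amount d, the differences among the four means do not depend on d, so the test rejects at its nominal level whatever d is. Simulated at a 5% level with d = 1.0 SD, the four-session test rejects in 5% of trials and the five-session test in 89%.

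**Best of four when nothing works.** The five session means are then exchangeable.

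- P(best active > sham) = 4/5 = 0.80.
- Mean apparent advantage = E[max of 4 standard normals] / √20 = 1.029 / 4.472 = 0.23 SD.
- 90th percentile of the apparent advantage (simulated) = 0.58 SD.

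**What a contrast with sham could show.** Take, as an example only, a one-sided 10% Dunnett bar.

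- Degrees of freedom: (20 − 1) × (5 − 1) = 76.
- Critical value: 1.86, which equals 1.86 × √(2/20) = 0.59 SD.
- With no true effect, at least one modality clears the bar in 10% of trials, by construction.

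Chance that at least one modality clears the bar:

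| True effect over sham | One modality works | All four work |
|---|---|---|
| 0.3 SD | 22% | 42% |
| 0.5 SD | 41% | 70% |
| 0.8 SD | 75% | 95% |

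**Dunnett or Tukey.** Extending Tukey to all ten pairs would also cover sham, but at a cost. At two-sided 5%, with all four modalities at 0.7 SD, at least one is declared better than sham in 57% of trials with Tukey (critical value 2.79) and 70% with Dunnett (2.49).

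**The case against.** The strongest reply is that the passages can be read together. Section 10.2 ties its disclaimer to efficacy as treatment of IBS-C, 10.2.2 is a subsection of it, and 10.1 concerns only acute distension pain. On that reading the hypothesis and the disclaimer address different things. This largely stands: the sentence in 10.2.2 is loose and does not by itself make 10.1 untestable.

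Nor does the plan rule out a sham comparison. Sham data are collected from every participant, 10.2 counts the placebo among the methods, and the ANOVA in 10.3 can be read as covering five sessions. A reader might infer that the plan cannot reach the answer none. The documents show only that no route to it is prespecified.

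A reader might also infer that a modality will go forward even if none beats sham. No rule says so, and 3.1 expressly allows none. What is missing is a stated criterion either way. Likewise, the 80% is a property of ranking under an exact null, not the error rate of any rule in the protocol.

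Finally, a pilot of 20 completers may reasonably rank rather than test. A hard 10% bar would leave no modality selected in about 59% of trials (100 − 41) when just one has a true effect of 0.5 SD. That is a good argument against imposing a gate. It is not an argument against estimating and reporting the contrast with sham.

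**Conclusion.** The point holds as a gap in the prespecified analysis. The objectives, hypothesis and design call for a comparison with sham, but section 10 counts four sessions where five are run, neither section 10 nor 10.3 names a modality-versus-sham contrast, and nothing in 10.2 says how a finding that none beats sham would be reached or used. The cause lies in the analysis text. The wording of 10.2.2 contributes only ambiguity, and rewording it alone would be clarification.

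The size can only be illustrated. With no true effect, the leading modality looks better than sham in 80% of trials, by 0.23 SD on average and by at least 0.58 SD in one trial in ten. The contrasts would be informative for large effects and weak for small ones. All of this rests on the assumed error model, 20 completers and effects in within-participant SD. The correction should be made because it uses data already being collected; whether to add a pass/fail threshold is a trade-off for the sponsor.

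**What to change.** 1. Sections 10 and 10.3: make the two texts agree, analyse all five sessions within participant, and prespecify the four modality-versus-sham contrasts of the pre-to-post change with Dunnett-adjusted intervals. The existing point and parameter contrasts can stay.
2. Section 10.1: state the hypothesis relative to sham, that is, that the pre-to-post change differs between at least one TEA condition and sham.
3. Section 10.2.2: limit the disclaimer to clinical efficacy in IBS-C, and say that the acute effect on distension-evoked sensation relative to sham is assessed.
4. Section 10.2: say that the chosen modality is reported together with its contrast against sham, and that none shown better than sham is a permitted conclusion. Any go/no-go threshold is for the sponsor to set; if one is set, it should be stated in advance with its pass rates at small as well as large effects.

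Cost: wording in five places and four more contrasts, with no added participants, visits or measurements. The pilot may end without supporting any modality.

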10.3 Final Analysis Plan

Analysis of variance (ANOVA) will be performed to investigate the difference in each of the outcomes among different sessions. Tukey's test will be used for study the differences in each of the measurements between two stimulation points (same stimulation parameters) and between two stimulation parameter sets (same stimulation points). The Pearson correlation analysis will also be performed to investigate the correlation between each of autonomic function parameters and the pain score or sensation threshold.

11 Source Documents and Access to Source Data/Documents

Only members of the study team will have access to source data. This includes: all information, original records of clinical findings, observations, or other activities in a clinical trial necessary for the reconstruction and evaluation of the trial.

12 Quality Control and Quality Assurance

- The study team will be present for each visit and follow the visit CRFs. The study team will go through the procedures with the GI physiology lab staff members to ensure that there is adherence to the protocol.
- The study team will sign the bottom of each study CRF at the end of the visit.

13 Ethics/Protection of Human Study participants

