Précis: This study aims to discern whether Transcutaneous Electrical Acustimulation (TEA) at acupuncture points ST36 and/or PC6 will relieve the abdominal pain associated with IBS-C. Each study participant will have 5 research visits at the Michigan Medicine GI physiology lab. During these visits, they will undergo a procedure similar to Anal Rectal Manometry performed by the GI physiology lab staff. TEA is similar to this procedure as it uses the barostat device and is performed by the GI physiology lab staff. This device has a rubber catheter that will be inserted 5-15 cm into the rectum of the study participant. Then the GI physiology staff will inflate the catheter. They will ask the study participant when they can sense the catheter. Then the GI physiology staff will continue to inflate the catheter and the study participants feel discomfort (described as the 'urge to defecate'). Then the study participant will be asked to pass the balloon (like they would pass a bowel movement).

The difference between ARM procedure and the study procedure is that there will be stimulation of acupuncture point ST36 which is below the knee cap or stimulation of acupuncture point PC6 which is just above the wrist.

At each visit there will be stimulation of only one of the points at either 100Hz or 25Hz. These are the potential combinations: ST36 100Hz, ST36-25Hz, PC6-100Hz, PC6-25Hz, Sham-TEA.

The frequency and position combination (or sham visit) is randomly assigned. The randomization determines the order in which the study participant moves through the study. Every study participant will, in the end, complete one visit at each frequency and a sham visit. The study participant will also complete surveys at the appointment. Study participants will be compensated for their participation and given a parking pass.

Objectives: Primary: Determine the best stimulation point and frequency for relieving the abdominal pain in study participants with IBS-C.

Secondary: Collect measurements of visceral hypersensitivity in study participants with IBS-C.

Population: 25 study participants, male and females, age ≥ 18 years, IBS-C satisfying Rome IV criteria

Phase: 1

Number of Sites:	1, Michigan Medicine, University of Michigan
Study Duration:	24 Months
Study participant Participation Duration:	Each visit will be 120 minutes long. There will be 5 visits total. The maximum amount of time between visits is 3 weeks. The minimum amount of time between visits is 1 week

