3.2.1 Primary Outcome Measures

The barostat device will measure the volume changes in the rectum during controlled distension of the gastrointestinal organs. If the TEA is successful, the study participant's maximum tolerance should increase after TEA compared to their first maximum tolerance of the visit. This will be defined by comparing their maximum tolerance pre and post TEA.

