5.4 Treatment Assignment Procedures

5.4.1 Randomization Procedures

Prior to the first visit, the order of TEA stimulation at the visits will be randomly assigned to each study participant. Every study participant will undergo every TEA combination (For example, ST36-100Hz, ST36-25Hz, PC6-100Hz, PC6-25Hz and Sham-TEA).

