8.1 Surveys

The study participant will complete the Rome IV criteria for Irritable Bowel Syndrome at the beginning of every visit. The study participant will complete the Visual Analog Scale Pain Score twice, once during both inflations, at every visit.

9 Assessment of Safety

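### The analysis text states no participant term and does not use the same-visit pre-TEA value as a covariate; adding both, with sham and the correlation unit specified, is a cheap gain in precision

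*Combined protocol and SAP*

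**What the plan says.** **Design.** The Précis states: "Every study participant will, in the end, complete one visit at each frequency and a sham visit". Section 5.4.1 repeats it: "Every study participant will undergo every TEA combination". Section 4 adds: "The placebo is the sham-TEA visit". Section 10.2.1 counts five sessions, and Section 10.2 counts four modalities and one placebo.

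**Measurements.** For the primary outcome, Section 3.2.1 expects maximum tolerance to rise relative to the first value of the visit and says: "This will be defined by comparing their maximum tolerance pre and post TEA". Section 8.1 says of pain: "The study participant will complete the Visual Analog Scale Pain Score twice, once during both inflations, at every visit". Under Section 4.1 the first inflation precedes TEA, the second is done with TEA running, and the ECG is recorded throughout.

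**Analysis.** The opening of Section 10 and Section 10.3 give the same three sentences with small differences. In Section 10.3, ANOVA will "investigate the difference in each of the outcomes among different sessions"; in the opening of Section 10 it will "investigate the difference in each of the outcomes among 4 different sessions". Tukey's test compares the two points at the same parameters and the two parameter sets at the same point. Pearson correlation examines "the correlation between each of autonomic function parameters and the pain score or sensation threshold". Neither place mentions a participant or repeated-measures term, a baseline covariate, the unit of the correlation, or a contrast with sham.

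**The concern.** Each participant serves as their own control twice: across the five visits and within each visit. The analysis text does not say how either feature is used. Section 10.2 says the pilot will decide which treatment goes into a future trial, so the precision of the comparisons among the four modalities is what the study has to deliver. With 20 completers and no preliminary data, a measurement already taken at every visit should not go unused.

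Three smaller gaps go with this. The unit of the Pearson correlation is open. The opening of Section 10 counts four sessions where the design has five. Sham is called the placebo, but no stated contrast uses it.

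**Working it through.** **Inputs from the documents.** 20 completers, 20% dropout, five conditions (Section 10.2). The plan's own figure reproduces: 20 / (1 − 0.20) = 25 enrolled. The 20 rests on experience, so there is no power calculation to reproduce.

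**Assumptions.** The documents give no SD, correlation, effect size or significance level. I take 5% two-sided and show a range of correlations.

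**Step 1: change against covariate adjustment, primary outcome.** Let r be the within-participant correlation of the pre and second-inflation values in the same visit, each with variance 1, and let change be uncorrelated between visits. The participant's overall level cancels.

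- Variance of change: 2(1 − r).
- Variance after adjustment for the pre value: 1 − r².
- Ratio: (1 − r²) / [2(1 − r)] = (1 + r)/2.

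This gives 0.65, 0.75 and 0.85 at r = 0.3, 0.5 and 0.7. Simulation (20,000 trials, 20 participants, slope estimated) gives slightly less gain because the slope has to be estimated:

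| r | Cut in contrast variance | Best modality first: change | Best modality first: adjusted |
|---|---|---|---|
| 0.3 | 34% | 87% | 94% |
| 0.5 | 24% | 87% | 92% |
| 0.7 | 14% | 87% | 89% |

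At r = 0.9 the variance cut is about 4%. The ranking columns assume one modality is 0.5 change-SD better than the other three and that the largest mean is chosen, a rule the plan does not state. In raw units the effect is 0.5 × √[2(1 − r)], that is 0.59, 0.50 and 0.39 SD. This is why the change column stays at 87%.

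**Step 2: participant term, outcomes analysed as levels.** If sessions were treated as independent, with between-session correlation 0.3, 0.5 and 0.7, the five-condition ANOVA would reject a true null in about 1.0%, 0.2% and under 0.1% of trials. With a participant term it rejects in about 5%. The error is on the conservative side and costs power. At correlation 0 nothing is lost. With complete data the participant term alone does not alter the order of the condition means.

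**Step 3: Pearson correlation.** With no true association and both variables clustered by participant (correlation 0.3, 0.5, 0.7):

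- 100 participant-sessions (20 × 5) pooled as independent: 9%, 17% and 26% false positives.
- Only one variable clustered: about 5%.
- One value per participant, or a repeated-measures correlation: about 5%.
- Five separate per-session tests: 5% each, but at least one false positive in about 19–23% of trials. For independent tests, 1 − 0.95⁵ = 22.6%.

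**Step 4: Tukey family.** Four active modalities give 6 pairs and a critical studentised range of 3.74. Five conditions give 10 pairs and 3.95 (both with a participant term). Putting sham into the Tukey family would therefore cost power on the point and frequency contrasts: at 0.8 SD, 64%, 82% and 97% with four levels fall to 60%, 78% and 97% with five, at between-session correlation 0.3, 0.5 and 0.7.

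**The case against.** The strongest reply is that nothing here is shown to be wrong. Repeated-measures ANOVA is the natural reading for a design in which everyone receives every condition. Change from the first inflation is the natural reading of Section 3.2.1 and is valid. Sections 10.2 and 10.2.2 disclaim any assessment of efficacy, so limiting the named contrasts to the active modalities fits the aim of selection. All of this stands.

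A reader might be tempted by five stronger readings. The documents do not support them.

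- *The plan treats sessions as independent.* It never says so, and the consequence would be conservative.
- *Change and the second-inflation level alone could name different winners for the primary outcome.* Section 3.2.1 requires a pre/post comparison, so level alone is not an available reading there.
- *The correlations will be inflated.* Only pooling would do that, and pooling is not stated.
- *Sham is dropped.* Section 10.3 gives no number of sessions, so its ANOVA can include sham. The four in the opening of Section 10 may mean the active modalities.
- *A visit term is required.* The order is randomised, so omitting one is not an error.

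What remains is that change uses the pre-TEA value less efficiently than adjustment does, and that the text leaves open choices that are better settled before the data are seen.

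**Conclusion.** This is a cheap improvement, of minor to should-fix severity. The main gain is in the primary outcome: contrast variance about 34%, 24% or 14% lower than with change, and the best modality ranked first 7, 5 or 2 percentage points more often, at assumed pre/post correlations of 0.3, 0.5 or 0.7. The gain fades as the correlation approaches 1. These sizes rest on assumed correlations, on change being uncorrelated between visits and, for the ranking, on an assumed 0.5 change-SD advantage. That adjustment is at least as precise as change, apart from the small cost of estimating the slope, does not depend on the particular correlation.

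The participant term, the unit of the correlation and the number of sessions are clarifications. They should be written down, but the text does not show that the wrong choice was intended.

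**What to change.** Make three changes in the opening of Section 10 and in Section 10.3.

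1. Analyse the value taken during or after TEA with a linear mixed model: condition (five levels, sham included), that visit's pre-TEA value, the participant's mean pre-TEA value and a random participant effect, using all available sessions. Take the point and frequency contrasts with Tukey adjustment over the four active modalities. Report each modality against sham separately, as an estimate with a confidence interval.
2. For the autonomic correlations, use one value per participant or a single repeated-measures correlation, which answers a within-person question. Do not pool sessions as independent, and do not run five per-session tests without multiplicity control.
3. Reconcile the four sessions in the opening of Section 10 with the five sessions of Section 10.2.1 and the sham placebo of Section 4.

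A visit term is optional.

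**Cost.** Wording and slightly more analysis work. No participants, visits or measurements are added, because tolerance and pain are already taken at both inflations and the ECG runs throughout. If pre and second-inflation values are uncorrelated, adjustment costs about 1% in variance compared with analysing the level alone. Using sessions from participants who do not complete assumes that their dropout is unrelated to the unseen values, given the data observed.

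### The trial is meant to choose one TEA combination, but section 10.3 names only four of the six active pairs, no sham contrast, and no rule for choosing

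*Combined protocol and SAP*

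**What the plan says.** **Purpose.** The primary objective in the Protocol Summary is: "Determine the best stimulation point and frequency for relieving the abdominal pain in study participants with IBS-C". Section 3.1 adds the aim of finding which combination, if any, reduces pain most. Section 10.2 says: "The findings of this pilot study will be used to determine which treatment to use in a future clinical trial". Section 10.2.2 says the pilot does not assess efficacy, so the choice of modality is its main product.

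**Design.** There are "4 different modalities and 1 placebo" (section 10.2). The active modalities are ST36 or PC6, each at 100 Hz or 25 Hz. Section 5.4.1: "Every study participant will undergo every TEA combination". The primary outcome (section 3.2.1) compares maximum tolerance before and after TEA within a visit.

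**Analysis.** Section 10.3 plans an ANOVA of each outcome across sessions, Tukey's test "between two stimulation points (same stimulation parameters) and between two stimulation parameter sets (same stimulation points", and Pearson correlations. The opening of section 10 has the same plan but counts four sessions; section 10.3 gives no number. Neither place gives a selection rule, a way to handle near-ties, or a required comparison with sham.

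**Size.** "The study team plans for a 20% participant dropout or incompletion rate", and "they will enroll 25 study participants when in actuality they need 20 study participants to complete the study". Also: "No preliminary data are available for the calculation of the sample size".

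**The concern.** The deliverable is a choice among four modalities, and the planned analysis is a set of significance tests that does not produce one. Three gaps combine.

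- The named comparisons leave out ST36-100Hz against PC6-25Hz and ST36-25Hz against PC6-100Hz. If the two best modalities form one of these pairs, no named comparison addresses the difference between them.
- Sham is a treatment session, yet no active-sham contrast is named. The proviso in section 3.1 that there may be no best combination cannot be addressed without one.
- No text links any pattern of results to a choice. The team would choose after seeing the data, and could do so on tolerance, pain score or ECG measures.

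At stake is whether the modality carried into the next trial was selected by a stated rule on the primary outcome, with an honest account of how sure the selection is.

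**Working it through.** **Inputs from the protocol.** Four active modalities and one sham (10.2); all conditions in every participant (5.4.1); 20 completers from 25 enrolled with 20% dropout (10.2); the named pairs (10.3).

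**Assumptions.** Familywise two-sided alpha 0.05; a repeated-measures error term (the form of the ANOVA is not stated); compound symmetry; 20 complete cases; no carryover. Effects are in within-participant residual SD. Dividing by √2 gives dz, the mean difference over the SD of the within-participant difference, so 0.5 SD is dz 0.5/1.414 = 0.35.

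**1. The plan's own figure.** 20 / (1 − 0.20) = 25. This reproduces the enrolment and is not in dispute. The 20 itself has no stated inputs.

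**2. Pair count.** Four active modalities give 4 × 3 / 2 = 6 pairs. Section 10.3 names two with the same frequency and two with the same point, which leaves two diagonal pairs. If all four modalities are equal, the observed top two form a diagonal pair in 2/6, or one third, of trials. With one leader over three equal others the share is also about a third.

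**3. Difference needed for a significant Tukey pair.** With four sessions, df = 3 × 19 = 57 and the critical |t| is 2.646. The threshold is 2.646 × √(2/20) = 0.837 SD. With sham in the family, df = 4 × 19 = 76 and the threshold is 2.794 × √(2/20) = 0.884 SD.

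**4. One modality leading three equal ones** (simulation, 40,000 trials per row, four-session Tukey family):

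| Lead (residual SD) | At least one named pair significant | Leader above both tested neighbours | Ranking picks the leader |
|---|---|---|---|
| 0.25 | 8% | 1% | 59% |
| 0.5 | 26% | 6% | 87% |
| 0.75 | 56% | 25% | 98% |
| 1.0 | 84% | 56% | nearly 100% |

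If all four are equal, ranking picks any given modality 25% of the time.

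**5. Sensitivity.** With a graded pattern (best, two halfway, worst), no named pair is significant in 87%, 78% and 57% of trials at ranges of 0.5, 0.7 and 1.0 SD. At 1.0 SD ranking picks the best in 90%. Putting sham in the Tukey family lowers the chance of any significant named pair under a single leader, for example from 50% to 44% at dz 0.5. Testing all six pairs does not make Tukey a selection method: the leader beats all three others in 2% of trials at dz 0.3 and 14% at dz 0.5.

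**6. Would 2×2 main effects do better?** That depends on the truth.

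- Additive, with a point effect of 0.5 SD: the main effect (Bonferroni for two) has 48% power, against about 15% for one Tukey pair and 28% for either pair.
- Single leader: each main effect is half the lead. At a lead of 0.5 SD its power is about 13%, against about 15% for one Tukey pair. At 1.0 SD it is about 47% against 69%.

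**7. Optimism of the winner.** The expected maximum of four equal means is 1.03 standard errors: 1.03 / √20 = 0.23 SD.

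**The case against.** **Significance is not made a condition for selection.** A reader might infer that Tukey is the trial's decision tool, so that a run without a significant pair leaves the team with no answer. No section says so. Section 10.2 says only that the findings will guide the choice, and observed means are findings. This objection stands; what remains is that no rule is stated and that Tukey is the only planned comparison between individual modalities.

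**The effect size is unknown.** A reader might also infer that the tests will usually separate nothing. The protocol gives no basis for that. Under a single leader it is true only below about 0.7 SD (dz about 0.5), and false at 0.75 SD. It lasts longer under a graded pattern.

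**Ranking and Tukey answer different questions.** Ranking always names someone; Tukey limits false claims. The 87% and 6% are therefore not rival success rates for one task. This stands as a caution. It does not rescue the plan, because the task the protocol sets is selection.

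**The same-point and same-frequency contrasts are defensible.** The objective is the best combination, and a single standout combination is an interaction pattern in which main effects lose power. This stands, so the Tukey pairs should not be replaced by main effects.

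**It is a pilot without an efficacy claim.** True, but choosing the modality is what this pilot is for.

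**Conclusion.** The concern holds in this form: the protocol makes selection its purpose, and section 10.3 names four of six active pairs, no active-sham contrast and no route from results to a choice. The change should be made.

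For a single leader of 0.25 to 1.0 residual SD with 20 completers, the named Tukey tests show it above both tested neighbours in about 1% to 56% of trials. Even then it has not been compared with its diagonal counterpart. A stated ranking rule would pick it in about 59% to nearly 100%. The range is an assumption, because the protocol supplies no effect size or SD, and the figures rest on the assumptions listed in the working. An ANOVA that ignored participant would use a different error term.

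The documents do not support saying that the trial will be unable to name a modality, or that the Tukey comparisons are an error in themselves.

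**What to change.** Amend section 10.3 as follows.

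1. Fit a within-participant model to all five sessions, and reconcile the four-session count at the start of section 10 with it.
2. State the rule: the selected modality is the active one with the largest mean rise in maximum tolerance, the primary outcome in section 3.2.1.
3. Report all six active differences and all four active-sham differences with intervals, and the bootstrap probability that the selected modality ranks first. These show how close any near-tie is.
4. In keeping with section 3.1, report the selected modality's difference from sham before calling it best. Sham has to enter here and not through the ranking: in complete cases, subtracting one sham mean from all four cannot change their order.
5. State that the winner's estimate is optimistic, by about 0.23 residual SD if all four are equal.
6. Keep the Tukey comparisons if wanted. A point-by-frequency model may be added as supportive, but should not replace the pairwise comparisons.

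The cost is analysis wording only: no added participants, visits or procedures. The downside is that a ranking rule names a winner even when the modalities are equal, so the ranking probability and intervals must always be reported with it.
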